4.5.3 Prohibited and Restricted Therapies

Patients may not use any of the following agents during the study:

- Any non-study anticancer or immunotherapy agent (investigational or non-investigational). **NOTE**: With approval of the IND Sponsor subjects may receive palliative radiation therapy as long as a site(s) disease outside of the radiation field is available to follow for response. No study drug should be given during radiation therapy.
- Concomitant use of valproic acid is prohibited due to its known activity as a HDAC inhibitor.
- CD137 or other immunologic activation agonists.
- Immunosuppressive agents.
- Chronic systemic corticosteroids at supraphysiologic doses.

NOTE: Subjects are permitted to use topical, ocular, intra-articular, intranasal, and inhalational corticosteroids (with minimal systemic absorption).

Physiologic replacement doses of systemic corticosteroids are permitted, in the absence of active autoimmune disease.

A brief course of corticosteroids for prophylaxis (e.g., contrast dye allergy), for treatment of non-autoimmune conditions (e.g., delayed-type hypersensitivity reaction caused by contact

allergen), and for treatment of infusion reactions and premedication (e.g., up to 25 mg IV hydrocortisone) is permitted.

Otherwise, steroid treatment should be completed at least 14 days prior to resuming studyrelated treatments unless approval to resume sooner is obtained from the IND Sponsor.

- Live vaccines (examples of live vaccines include, but are not limited to: measles, mumps, rubella, chicken pox, yellow fever, rabies, BCG, and typhoid [oral] vaccine). Seasonal influenza vaccines for injection are generally killed virus vaccines and are allowed. However, intranasal influenza vaccines (e.g. Flu-Mist®) are live attenuated vaccines, and are NOT allowed.
- The use of anticoagulants is known to increase the risk of gastrointestinal hemorrhage. Since gastrointestinal hemorrhage is an adverse reaction with nivolumab, subjects who require concomitant anticoagulant therapy should be monitored closely.
- Concomitant use of the drugs below with entinostat should be avoided during the study (also listed in **Appendix E**):

• Sensitive substrates of CYP1A2, CYP2C8, CYP3A with a narrow therapeutic window • Drugs that are known to inhibit or induce P-gp

4.5.4 Precautions

Combination therapy may result in unexpected toxicity especially in novel combinations with other immune modifying agents. A striking example in macaques is presented in Vaccari, et al. 2012 [120].

4.6 Definition of an Overdose for this Protocol

An overdose is defined as the accidental or intentional administration of any dose of a product that is considered both excessive and medically important. All occurrences of overdose must be reported as SAEs (see Section 6.6).

4.7 WOCBP, Contraception, Use in Pregnancy, Use in Nursing

4.7.1 WOCBP

A WOCBP is defined as any female who has experienced menarche and who has not undergone surgical sterilization (hysterectomy or bilateral oophorectomy) and is not postmenopausal. Menopause is defined as 12 months of amenorrhea in a woman over age 45 years in the absence of other biological or physiological causes. In addition, women under the age of 55 years must have a serum follicle stimulating hormone (FSH) level > 40mIU/mL to confirm menopause. Women treated with hormone replacement therapy (HRT) are likely to have artificially suppressed FSH levels and may require a washout period in order to obtain a physiologic FSH level. The duration of the washout period is a function of the type of HRT used. The duration of the washout period selow are suggested guidelines and the investigators should use their judgment in checking serum FSH levels. If the serum FSH level is >40 mIU/ml at any time during the washout period, the woman can be considered postmenopausal:

- 1 week minimum for vaginal hormonal products (rings, creams, gels)
- 4 week minimum for transdermal products
- 8 week minimum for oral products

4.7.2 Contraception

The investigational agents used in this protocol may have adverse effects on a fetus in utero. Furthermore, it is not known if the investigational agents have transient adverse effects on the composition of sperm. Non-pregnant, non-breast-feeding women may be enrolled if they are considered highly unlikely to conceive. Highly unlikely to conceive is defined as 1) surgically sterilized, or 2) postmenopausal, or 3) amenorrheaic for <2 years without a hysterectomy and oophorectomy and with a documented FSH value in the postmenopausal range, or 4) not heterosexually active for the duration of the study, or 5) heterosexually active and willing to use 2 methods of birth control (which is also required for the female partners of male subjects). The 2 birth control methods can be 2 barrier methods or a barrier method plus a hormonal method to prevent pregnancy, used throughout the study starting with Visit 1 through 5 months after the last

dose of study medication. Male subjects enrolled in this study must also agree to use an adequate method of contraception starting with Visit 1 through 7 months after the last dose of study drug.

Investigators shall counsel WOCBP and male subjects who are sexually active with WOCBP on the importance of pregnancy prevention and the implications of an unexpected pregnancy. Investigators shall advise WOCBP and male subjects who are sexually active with WOCBP on the use of highly effective methods of contraception. Highly effective methods of contraception have a failure rate of < 1% per year when used consistently and correctly.

4.7.2.1 Highly Effective Methods of Contraception

- Male condoms with spermicide.
- Hormonal methods of contraception including combined oral contraceptive pills, vaginal ring, injectables, implants, and intrauterine devices (IUDs) such as Mirena by WOCBP subject or male subject's WOCBP partner.
- Nonhormonal IUDs, such as ParaGard.
- Tubal ligation.
- Vasectomy.
- Complete abstinence.

Complete abstinence is defined as complete avoidance of heterosexual intercourse and is an acceptable form of contraception for all study drugs. Abstinence is only acceptable when this is in line with the preferred and usual lifestyle of the subject. Periodic abstinence (e.g., calendar, ovulation, symptothermal, profession of abstinence for entry into a clinical trial, post-ovulation methods) and withdrawal are not acceptable methods of contraception. Subjects who choose complete abstinence are not required to use a second method of contraception, but female subjects must continue to have pregnancy tests. Acceptable alternate methods of highly effective contraception must be discussed in the event that the subject chooses to forego complete abstinence. NOTE: If a patient has a positive or indeterminate serum or urine pregnancy test, then

an ultrasound must be done to rule out pregnancy to enroll on trial. A serum B-HCG value of <25 is considered a negative pregnancy test.

Subjects should be informed that taking the study medication may involve unknown risks to the fetus (unborn baby) if pregnancy were to occur during the study. In order to participate in the study they must adhere to the contraception requirement (described above) for the duration of the study. If there is any question that a subject will not reliably comply with the requirements for contraception, that subject should not be entered into the study.

4.7.3 Use in Pregnancy

The investigational agents used in this protocol may have adverse effects on a fetus; therefore, women with a positive pregnancy test at screening will not be eligible for enrollment. If a subject inadvertently becomes pregnant while on treatment, the subject will immediately be removed from the study treatment. The study team will contact the subject at least monthly and document the subject's status until the pregnancy has been completed or terminated.

The investigator must immediately notify the Syndax Sponsor and BMS of any pregnancy using the Pregnancy Surveillance Form within 24 hours of notification and in accordance with the SAE reporting procedures described in Section 6.5. Any pregnancy that occurs in a female partner of a male study participant should also be reported to the Syndax and BMS.

Protocol required procedures for study treatment discontinuation and follow-up must be performed on the subject unless contraindicated by pregnancy (e.g. x-ray studies). Other appropriate pregnancy follow-up procedures should be considered if indicated.

Follow-up information regarding the course of the pregnancy, including perinatal and neonatal outcome and where applicable, offspring information must be reported on the Pregnancy Surveillance Form.

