3. PATIENT SELECTION

3.1 Eligibility Criteria

- **3.1.1.** Patients must have histologically or cytologically confirmed cholangiocarcinoma or pancreatic adenocarcinoma that is metastatic or unresectable and has progressed despite standard therapy or is intolerant of therapy; 1 or 2 prior chemotherapy regimens in the metastatic setting or progression < 6 months from the completion of adjuvant chemotherapy.
- **3.1.2.** Age ≥18 years.
- **3.1.3.** ECOG performance status of 0 or 1 (Karnofsky \geq 70%, see Appendix A).
- **3.1.4.** Life expectancy of greater than 12 weeks.
- **3.1.5.** Patients must have normal organ and marrow function as defined below:
 - Hemoglobin (HgB) $\geq 9.0 \text{ g/dL}$
 - Leukocytes \geq 3,000/mcL
 - Absolute neutrophil count $\geq 1,500/mcL$
 - Platelets $\geq 100,000/mcL$
 - Total bilirubin ≤ 1.5 x institutional upper limit of normal (ULN); an exception to this may be allowed for participants with Gilbert's syndrome with documented approval by the Protocol Chair
 - AST(SGOT)/ALT (SGPT) $\leq 3 \times$ institutional ULN
 - Creatinine within normal institutional limits

or

• Creatinine clearance ≥ 60 mL/min using the Modified Cockcroft-Gault, as the formula below:

Female CrCl = (140 - age in years) x weight in kg x 0.85

72 x serum creatinine in mg/dL

Male CrCl = (140 - age in years) x weight in kg x 1.00

72 x serum creatinine in mg/dL

- **3.1.6.** Negative *(serum or urine)* pregnancy test, for women of childbearing potential. NOTE: If a patient has a positive or indeterminate serum or urine pregnancy test, then an ultrasound must be done to rule out pregnancy to enroll on trial. A serum B-HCG value of <25 is considered a negative pregnancy test.
- **3.1.7.** Patients must have measurable disease per RECIST 1.1. (see Section 8.1)
- **3.1.8.** Patient must have an accessible non-bone tumor lesion from which serial core biopsy specimens can be obtained.

NOTE: Patients with bone only disease are not eligible due to difficulties in obtaining serial bone biopsies for correlative analyses.

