- **3.1.9.** Women of child-bearing potential (WOCBP) and men must agree to use adequate contraception (hormonal or barrier method of birth control; abstinence) prior to study entry and during all the period of study participation for at least 5 months following the last dose of nivolumab (see Section 4.7.2). WOCBP must have a negative serum or urine pregnancy test (minimum sensitivity 25 IU/L or equivalent units of HCG) at baseline. Women must not be breastfeeding. Women who are not of childbearing potential (e.g., who are postmenopausal or surgically sterile as well as azoospermic men) do not require contraception. NOTE: If a patient has a positive or indeterminate serum or urine pregnancy test, then an ultrasound must be done to rule out pregnancy test.
- **3.1.10.** Willingness to provide tissue and blood samples for mandatory translational research.
- **3.1.11.** Ability to understand and the willingness to sign a written informed consent document.

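### The pregnancy rules contradict each other: 4.7.3 omits the ultrasound exception, 3.1.9 read alone asks for less contraception than 4.7.2, the 6.5 reporting window is ambiguous, and 6.2.4 and 6.5 differ on whether pregnancy is an SAE (minor)

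*Combined protocol and SAP*

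**What the plan says.** **Positive test.** Section 4.7.3 says "women with a positive pregnancy test at screening will not be eligible for enrollment" and gives no exception. For a positive or indeterminate test, 3.1.6 says "then an ultrasound must be done to rule out pregnancy to enroll on trial". Section 4.7.2.1, just before 4.7.3, repeats that "an ultrasound must be done to rule out pregnancy to enroll on trial", and so does the calendar text under footnote 13.

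**Contraception.** Under 3.1.9, women of child-bearing potential "and men must agree to use adequate contraception (hormonal or barrier method of birth control; abstinence"), "for at least 5 months following the last dose of nivolumab", with a reference to 4.7.2. Section 4.7.2 accepts a woman who is "heterosexually active and willing to use 2 methods of birth control (which is also required for the female partners of male subjects"). The two methods are to be "used throughout the study starting with Visit 1 through 5 months after the last" dose of study medication. Men "must also agree to use an adequate method of contraception starting with Visit 1 through 7 months after the last dose of study drug". Section 4.7.2.1 exempts complete abstainers from a second method and makes adherence to the contraception requirement a condition of taking part.

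**Reporting.** Section 6.5 covers pregnancies in a patient that are spontaneously reported to the investigator. It joins three limits: during the study, within 120 days of completing it, or 30 days after treatment stops if new anticancer therapy begins. The earliest is to govern. Section 4.7.3 requires notification of any pregnancy, and of partner pregnancies, with no end date, and refers to 6.5 for the procedure.

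**SAE status.** Section 6.2.4 lists pregnancy among the serious criteria. Section 6.5 says pregnancy is not an adverse event and makes only pregnancy losses SAEs.

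**The concern.** The protocol states that the study drugs may harm a fetus, so these rules should give one answer wherever a site looks, and they do not. A woman with a positive test and a negative ultrasound is eligible under 3.1.6 and ineligible under 4.7.3, so enrolling her could be logged as a violation. A site that screens from the eligibility list alone could accept a woman on one method, or tell a man to stop at 5 months. A pregnancy conceived while the protocol still requires contraception might not be reported if a site applies the 30-day limit in 6.5. What is at stake is fetal safety and correct enrolment in a small number of patients.

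**Working it through.** The plan gives no figure of its own on this point, so there is none to reproduce. The check compares the sections and then counts days.

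**(a) Positive test.** Items 3.1.6 and 3.1.9 both start from a negative test. 3.1.6 adds the ultrasound route in a note, and 3.1.9 carries a garbled copy of that note. Sections 4.7.2.1 and the calendar agree with 3.1.6. Exclusion 3.2.9 bars pregnant women, not women with a positive test. Section 4.7.3 is the only outlier.

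**(b) Contraception.**

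| | 3.1.9 read alone | 4.7.2 |
|---|---|---|
| Methods, heterosexually active women | one (hormonal or barrier) | two |
| Methods, female partners of male patients | not stated | two |
| Duration, women | at least 5 months | 5 months |
| Duration, men | at least 5 months | 7 months |
| Clock starts at | last nivolumab dose | last dose of study drug |

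Taking a month as 365.25/12 = 30.44 days (assumption), 5 months is 152.2 days and 7 months is 213.1 days. The shortfall for men is 213.1 − 152.2 = 60.9 days. For women the months agree and only the starting point differs. Weekly entinostat could run about 3 weeks past the last nivolumab dose on the 4-weekly schedule.

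**(c) Reporting window for a female patient.** Gap = max(0, 152.2 − day on which the 6.5 window closes), counted from the last dose. Completing the study is not defined in 6.5. Section 4.10 puts the end-of-treatment (EOT) visit at day 28 ± 7.

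| Reading | Window closes | Gap |
|---|---|---|
| New therapy starts, 30-day limit governs | day 30 | 122.2 days |
| No new therapy, 120 days from last dose | day 120 | 32.2 days |
| No new therapy, 120 days from EOT at day 21 | day 141 | 11.2 days |
| No new therapy, 120 days from EOT at day 28 | day 148 | 4.2 days |
| No new therapy, 120 days from EOT at day 35 | day 155 | 0 |
| During the study includes survival follow-up | after day 152 | 0 |
| 4.7.3 read as having no time limit | none | 0 |

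The survival-follow-up reading has textual support: 4.8 separates stopping treatment from leaving the trial, and calendar footnote 23 keeps contact for up to 2 years. It also leaves the 30-day limit with almost no role, so a site cannot be sure it was intended. No gap is computed for partners, because 6.5 covers only pregnancy in a patient and 4.7.3 sets no window.

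**(d) SAE status.** The 24-hour reporting time is the same in 4.7.3, 6.4 and 6.5, so the label does not change speed. It does decide whether the SAE collection period in 4.10 and 6.3 could be applied to a pregnancy.

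**Do the existing contacts cover the periods?** With EOT at day 28 and contacts every 91 days (± 14), the nominal days are 28 + 91 = 119, 28 + 182 = 210 and 28 + 273 = 301. The second contact falls no earlier than 21 + 182 − 14 = day 189, after day 152. For men the second contact, at about day 210, can precede day 213. The third falls no earlier than 21 + 273 − 14 = day 280.

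**The case against.** The strongest reply is that a careful reader can reconcile most of this. Several stronger inferences do fail:

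- *A patient may take part on one method, or a man stop at 5 months.* Not supported. 3.1.9 sets a floor and cites 4.7.2, and 4.7.2.1 makes the contraception requirement a condition of participation. The remaining fault is that the eligibility item, read alone, states less than the rule that binds.
- *Women are given a shorter period in 3.1.9.* Not supported. Both sections say 5 months.
- *There is a definite 122-day hole in reporting.* Not supported. That figure needs new therapy and the 30-day limit. Section 4.7.3, read without a time limit, closes the gap, and so does counting survival follow-up. Neither reading is excluded, but neither is stated.
- *The SAE window fixes the gap.* Applying the SAE period of 100 days, or 30 days after new therapy starts, would leave a gap of 52 days or more. But 6.5 gives a window specific to pregnancy, so the SAE period matters only if pregnancy itself is an SAE, which is the unresolved question.
- *The windows are required to match.* No text says so. The reason to align them is that the protocol itself sets 5 and 7 months as the periods in which conception must be avoided.

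On the positive test, it is fair to say that the purpose of 4.7.3 is to protect a fetus and that a woman without one falls outside it. Its wording still excludes her. The label dispute in (d) is real but does not affect reporting speed.

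**Conclusion.** The point holds as a minor error in current wording. Four sets of stated rules conflict or are ambiguous:

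- eligibility after a positive test;
- contraception in 3.1.9 against 4.7.2 (one method against two; for men 5 against 7 months, about 61 days);
- the 6.5 window (about 122 days short if new therapy starts and the 30-day limit governs, 0 to about 32 days without new therapy, none on two other readings);
- the SAE status of pregnancy.

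The day counts assume 30.44-day months and that treatment stops at the last dose. Few patients are likely to be affected, although the documents give no age or sex distribution. The response-rate analysis does not change.

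**What to change.** - **4.7.3:** add an exception where ultrasound rules out pregnancy, with a reference to 3.1.6.
- **3.1.9:** restate to match 4.7.2. Women of child-bearing potential: two methods, except with complete abstinence, through 5 months after the last dose of study drug. Men: an adequate method through 7 months, with female partners using two methods.
- **6.5:** require reporting through at least 5 months after the last dose for patients and 7 months for partners of male patients, whether or not new anticancer therapy starts.
- **Follow-up:** ask about pregnancy at the existing 3-monthly contacts (4.10, calendar footnote 23). The first two cover the 5-month period for women, and a third is needed for men to pass 7 months.
- **6.2.4 and 6.5:** state in both whether pregnancy itself is an SAE, and keep the 24-hour reporting time.

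The cost is protocol wording, approved by the IRB as section 11.3 requires for any amendment, and one added question at contacts already planned. No visit or procedure is added.

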4.7.4 Use in Nursing Women

Since many drugs are excreted in human milk, and because of the potential for serious adverse reactions in the nursing infant, subjects who are breast-feeding are not eligible for enrollment.

4.8 Duration of Treatment and Criteria for Removal from Treatment

In general, treatment will continue until one of the following criteria are met:

- Disease progression. **NOTE**: Treatment may continue under the guidelines discussed in **Section 4.9**, as per opinion of the Investigators.
- The patient or legal representative (such as a parent or legal guardian) withdraws consent for treatment but not follow up.
- Intercurrent illness that prevents further administration of treatment.
- Unacceptable adverse events. If the study treatment has provided clinical benefit, the IND sponsor may approve trial continuation for patients experiencing entinostat-related toxicities that are not life threatening or of major clinical concern (such as pruritis or rash).
 NOTE: Assessment for discontinuation of entinostat may be made independently of nivolumab, continuation of entinostat may be considered with approval by the IND sponsor. There are instances where treatment with nivolumab may continue if entinostat has been discontinued. (Section 5.1)
- If in the opinion of the Investigator, a change or temporal or permanent discontinuation of therapy would be in the best interest of the patient. The Sponsor should be included in this decision.
- Noncompliance with trial treatment or procedure requirements.
- Patient becomes pregnant. All women of child bearing potential should be instructed to contact the investigator immediately if they suspect they might be pregnant (e.g., missed or late menstrual period) at any time during study participation. The investigator must immediately notify CTEP in the event of a confirmed pregnancy in a subject participating in the study.
- Treatment required with other chemotherapeutic or investigational anti-neoplastic drugs.

- Patient is lost to follow-up.
- In the case that a participant develops intolerance or side effect that is attributable to entinostat, the participant may, at his or her discretion, continue to receive only Nivolumab as otherwise indicated as long as they have received at least 1 full dose of both entinostat and nivolumab and nivolumab re-treatment criteria are met as outlined above.
- If nivolumab has to be permanently discontinued because drug-related toxicity, the patient will be permanently discontinued from entinostat treatment too.

The subject must be discontinued from the trial for any of the following reasons:

- The patient or legal representative (such as a parent or legal guardian) withdraws consent for follow-up.
- Termination of the study.
- Patient is lost to follow up.

The reason for study removal and the date the subject was removed must be documented in the Case Report Form.

4.9 Treatment Beyond Progression

A minority of subjects treated with immunotherapy may derive clinical benefit either delayed responses, stable disease, or increased overall survival despite initial evidence of progressive disease (PD) with nivolumab or combination treatment.

Subjects may be permitted to continue treatment beyond initial RECIST 1.1-defined PD as long as the following criteria are met:

• Patients must be clinically stable with no change in performance status due to disease progression.

- No indication for immediate alternative treatment
- Patient [assessed by the investigator] is showing clinical benefit and tolerates study drug. The assessment of clinical benefit should take into account whether the subject is clinically stable or deteriorating and likely or unlikely to receive further benefit from continued treatment
- The time of progression is noted from the first assessment that exceeds standard criteria All decisions to continue treatment beyond initial progression must be discussed with the PI in advance, including if for any exception to the criteria noted above.

New lesions are considered measurable at the time of initial progression if the longest diameter is at least 10 mm (except for pathological lymph nodes, which must have a short axis of at least 15 mm). Any new lesion considered non-measurable at the time of initial progression may become measurable and therefore included in the tumor burden measurement if the longest diameter increases to at least 10 mm (except for pathological lymph nodes, which must have an increase in short axis to at least 15 mm).

For statistical analyses that include the investigator-assessed progression date, subjects who continue treatment beyond initial investigator-assessed, RECIST 1.1-defined progression will be considered to have investigator-assessed progressive disease at the time of the initial progression event. Subjects who have tumor shrinkage following RECIST-defined progression (e.g., irRC) will be also summarized separately.

